Severe	Causes marked limitation in activity; some assistance is usually required; medical intervention or therapy is required; hospitalization is probable.	

The PI is ultimately responsible for assessing and reporting all adverse events as outlined in the protocol. The assessment of AEs may be delegated to a medically qualified Sub-Investigator, trained on this study protocol, who is listed on the FDA Form 1572 or equivalent document, and on the delegation of authority form. The PI or investigator will report adverse events to the IRB in accordance with IRB guidelines.

Reporting of Serious Adverse Events

All SAEs will be reported to UMass by the PI through telephone or email within 24 hours of discovery, using the form provided by the lead site, UMass. In the event of a SAE, the PI or designee will notify the lead site PI, [name] by phone or email within 24 hours of the event and will email supporting documentation within 48 hours of the event and then as relevant data is available within the following week.

The PI must inform the IRB immediately regarding any AE (does not have to be causally related) that is both serious and unexpected; or that represents a series of AEs that, on analysis, is unanticipated, or occurs at an unanticipated frequency, or otherwise represents an unanticipated safety risk to the study subject. The IRB may subsequently choose to modify the informed consent or request changes to the protocol.

Occasionally, after a patient completes the study, a piece of data is missing or that we come to understand that it would be helpful to ask an additional question of all participants. For this reason, participants will be asked as part of the consent process if they are willing to be contacted after their study participation ends.

Protocol Deviations and Waiver

Protocol Waivers

Protocol waivers will be considered on a case by case basis by the principle investigator for this study.

Procedure for Non-Compliant Subjects

Problems related to symptoms of schizophrenia and substance dependence can cause a number of challenges to carrying out the protocol with a given participant, including: missed appointments, visits outside of the window, inability to complete all study assessments, not taking medication correctly, and not returning medication containers and extra pills. Such events will not be considered protocol deviations unless they impact a participant's safety or the scientific validity of the study.

Subjects who miss a study visit will be allowed (at the discretion of the PI) to make up that visit within that week. Subjects who withdraw consent will no longer have data collected for the study.

Protocol Deviation

Major and Minor Protocol Deviation

	Major Protocol Deviation	Minor Protocol Deviation
Definition	A deviation that may : Impact subject safety, Affect the integrity of study data, and/ or Affect the subject's willingness to participate in the study.	A deviation that does not : Impact subject safety, Compromise the integrity of study data, and/ or Affect the subject's willingness to participate in the study.
Examples (not all- inclusive)	Failure to obtain informed consent	Implementation of unapproved recruitment procedures
	Informed consent obtained by an unauthorized individual	Only a photocopy of the signed/ dated consent form is available (the original is missing)
	Enrollment of a subject who did not meet eligibility criteria for whom a protocol exception was not obtained	Pages are missing from the signed/ dated informed consent form
	Performing a study procedure that is not approved by the IRB and/or is not in the protocol	Use of invalid consent form (i.e. without IRB approval or outdated/expired form)
	Failure to perform a required lab test that, in the opinion of the Site Investigator, may affect	Study procedure conducted out of sequence
	subject safety or data integrity	Failure to perform a required lab test
	Failure to perform or follow a study procedure that, in the opinion of the Site Investigator,	Missing lab results

	may affect subject safety or data	Over-enrollment		
	integrity			
	integrity	Examples and of a chicade offer IDD		
		Enrollment of subjects after IRB		
	Failure to follow safety (AE)	approval of the study has expired		
	management plan			
	management plan			
		Failure to submit a continuing		
	Failure to report a SAE to the	review application to the IRB		
	IRB and/or Coordination Center	before study expiration		
Reporting	Record the date discovered, date	Record the date discovered, date		
Requirements	occurred, description of event in	occurred, description of event in		
	the Protocol Deviation Log.	the Protocol Deviation Log.		
	Notify the UMass within 24	Notify UMass.		
	hours.	Report to local IRB as per		
	Report to local IRB	institutional policy		

I. DOCUMENTATION OF DATA

Case Report Forms

The case report forms (CRF) will be collected using an electronic data capture (EDC) system RedCap. The study team will document subject data with paper CRF individual subject binders which will serve as the source data. The data entry on RedCap will be completed by designated study staff. This should be completed soon after the subject completes the study visit.

Data will be stored on the REDCap servers within the regulated environment at UMass Medical School (UMMS). REDCap servers are maintained by Information Technology and includes physically secure and electronically protected portion of the data center with its own insulated network space labeled "the Regulated Environment" to provide a secure environment for the storage and handling of sensitive electronic data including protected health information (PHI) and protected personal information (PPI). The Regulated Environment is securely housed within the IT data center meaning physical access is limited to only those IT professionals employed by IT with a job related need and with proper electronic identification. The servers are backed up nightly, properly updated and patched, protected with anti-virus and anti-spyware software.

Electronic access to sensitive data resources within the regulated environment is controlled using the highest standard of proven network architecture. Data will be transferred into the regulated environment via direct data entry, controlled web interface form-fill-out into a REDCap database.

Data Capture, Review and Validation

Study specific data that has been outlined in the protocol will be entered into the clinical database via the EDC system by designated site staff in accordance with the eCRF

Completion Guidelines. Data is verified electronically using a series of on-line programmed edit checks that have been created by the clinical data manager and programmed by the clinical data programmer or designee. Data discrepancies will be brought to the attention of the site staff and investigated by the clinical monitor and site study coordinator. The clinical monitor(s) will review and verify all eCRF data against acceptable source documentation during scheduled monitoring visits. The clinical monitor will work closely with the site study coordinator to address any discrepancies which have been found so that resolutions can be made and documented into the clinical database.

Database Quality Assurance

The clinical database will be reviewed and checked for omissions, apparent errors, and values requiring further clarification using computerized and manual procedures. Data queries requiring clarification will be generated and addressed by the investigational site.

This study will be organized, performed, and reported in compliance with the protocol, SOPs, working practice documents, and applicable regulations and guidelines.

Record Retention

All documents pertaining to the study, including all versions of the approved study protocol, copy of the informed consent document and Health Insurance Portability and Accountability Act (HIPAA) documents, eCRFs, source documents (i.e., subject records, hospital records, laboratory records, medication records, etc.), and other study-related documents will be retained at the study site for 5 years after the study ends.

The PI must notify and obtain approval in writing from the UMass prior to destruction of any study records or provide an opportunity for the UMass to collect such records. If the Investigator withdraws from the study (e.g., relocation, retirement) all study-related records should be transferred, in a written agreement with UMass, to a mutually agreed upon designee and specified timeframe.

Data Confidentiality

Potential risks to data confidentiality will be mitigated by requirements for the deidentification of all study data and by security protocols for all data capture systems. All users of the EDC system will be tracked and provided access in a secure fashion following established SOPs for this process.

As with all research data, information gathered by the study will be used only for aggregate analysis; it will not be released with any information that identifies research participants. Pharmacogenetic information, in particular, will be coded and unlinked to

individual respondent identifiers. The lead study site will apply for a Certificate of Confidentiality in order to ensure the complete anonymity of subjects with regards to their drug use. If approved, the Certificate of Confidentiality will be extended to all other study sites. If and when a Certificate of Confidentiality is approved and extended for all sub-sites, language specifying this Certificate will be added to the Informed Consent Form.

Uses and risks related to data collection will be outlined in the informed consent and reviewed with the subjects.

J. MONITORING AND OVERSIGHT

Initiation of Study Sites

Prior to subject enrollment, site initiation visits will be conducted by UMass at all sub sites. The initiation visit is completed to ensure IRB approval is obtained and documented; all study staff are trained and clearly understand the protocol.

Site Monitoring

Through the study the lead site UMass will conduct investigational site monitoring to ensure overall quality and compliance with protocol and applicable regulations by all investigators. Such monitoring activities will be conducted on-site and remotely including telephone calls and emails. The site will receive notification prior to the on-site monitoring visit. The investigator and the study staff are expected to be available on the day of site visit to address any queries. During the on-site study visits, subject case report forms (CRFs) will be reviewed for completeness and protocol compliance.

Study Closeout Visit

Upon completion of the study, a study closeout visit will be completed to review all study files and regulatory documents. The monitor will ensure all regulatory documents are up-to-date and complete. All study documents should be retained for an appropriate time period as stated in the contract.

Other issues which will be reviewed at this visit include: possibility of site audits, publication policy, and ensuring that the Investigator will notify the local IRB regarding study closeout.

Medical Monitoring

The medical monitor for this trial will be a board certified psychiatrist designated by the lead site, UMass. The Medical Monitor will review all adverse events, review issues

related to subject eligibility, assess the benefits and risks of protocols on an ongoing basis, and work in collaboration with the IRB to identify safety signals and trends.

K. ETHICAL CONSIDERATIONS

Ethics Review

The study protocol, ICF and all relevant documents will be reviewed and approved by the local IRB prior to study initiation. A written IRB approval from the committee must be received by UMass before starting study enrollment. The protocol must be re-approved by the IRB upon receipt of protocol amendments and annually, as part of their IRB regulatory requirements and institutional procedures. The PI or designee is responsible for submitting all protocol changes, SAE reports, administrative letters etc. to the IRB according to their regulatory policies.

Ethical Conduct of the Study

The study will be conducted as per the protocol and will adhere to the GCP standards. The investigators and all study staff should be trained in GCP guidelines.

Informed Consent

The PI must ensure to clearly explain and provide oral and written information on the study purpose, procedures, risks and benefits of participating (including potential risks involving the study medications) to each subject and/or legal guardian. All information should be provided in language that is easy to understand. All subjects must be informed that their participation is voluntary and they can withdraw from the study at any time if they choose. If the subject chooses to participate, he/she or legal guardian must sign the informed consent form and when required, the caregiver must sign the caregiver ICF. Any questions, concerns, or ambiguities will be clarified by the site's PI or another study clinician prior to the patient signing consent.

L. STATISTICS AND DATA ANALYSIS

Intent-to-treat analysis and a mixed model approach will be conducted to estimate the pragmatic effects of brexpiprazole treatment on the number of days of substance use in the past week, substance craving, psychiatric symptoms and quality of life. The entire 12 week duration of treatment, including the 6-week switchover phase, will be included in the analysis. Polynomial time trends (e.g., slopes) will be used to fit the population mean response curve for the control group. Group-by-time interactions will be modeled as a function of time to fit between-group effects. Subject-specific parameters will be estimated to model individual subject deviations from the group mean. Baseline measures of substance use and clinical symptoms will also be included in the model as covariates.

REFERENCES

3. van Dijk D, Koeter MW, Hijman R, Kahn RS, van den Brink W. Effect of cannabis use on the course of schizophrenia in male patients: a prospective cohort study. Schizophr Res. 2012; 137(1-3): 50-7.

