- 2) Meets the DSM-5 criteria for diagnoses of schizophrenia or schizoaffective disorder and substance use disorder (alcohol, cocaine, heroin, or cannabis) based on the Mini International Neuropsychiatric Interview (MINI).
- 3) Uses substance on at least 4 of the previous 30 days prior to randomization with at least one use in the week prior to randomization for one of the substances (cocaine, heroin, marijuana or alcohol) as assessed by the TLFB interview
- 4) Stable dose of antipsychotic agent for at least one month
- 5) Well established compliance with outpatient medications
- 6) Female subjects of child-bearing potential are required to practice appropriate birth control methods during the study.
- 7) Male subjects who are sexually active must agree to use appropriate birth control measure to avoid partner pregnancy

Exclusion criteria:

Each subject must not have the following exclusion criteria prior to randomization in the study.

- 1) Psychiatrically unstable
- 2) Currently meets DSM-5 criteria for any substance use disorder other than caffeine, nicotine, alcohol, cocaine, heroin and cannabis.
- 3) Significant, unstable medical conditions including severe cardiovascular, hepatic, renal or other medical diseases
- 4) History of a seizure disorder
- 5) Pregnancy or breastfeeding
- 6) Currently on aripiprazole or cariprazine
- 7) Currently on medications to treat substance use (disulfiram, naltrexone, acamprosate, methadone, buprenorphine, varenicline or bupropion)
- 8) Patients previously exposed to brexpiprazole

Exclusionary Lab values:

Comprehensive Metabolic Panel					
Sodium	<1.1 times the lower limit or >1.1 times upper				
limit of the reference range					

Potassium	<1.1 times the lower limit or >1.1 times upper limit of the reference range
Blood Urea Nitrogen (BUN)	>1.3 times upper limit of the reference range
Creatinine	>1.3 times upper limit of the reference range
Aspartate amino transferase (AST)	>3 times upper limit of the reference range
Alanine amino transferase (ALT)	>3 times upper limit of the reference range
Glycated Hemoglobin (HbA1c)	Patients with a value > 9.0% (at screening only)
eGFR	< 35 ml/min

E. SCHEDULE OF EVENTS AND STUDY ASSESSMENTS

Table 1. Schedule of Events

Procedu re	Visit	Screening	Visit 1 (basel ine)	Visit 2	Visit 3	Visit 4	Visit 5	Visit 6	Visit 7	Visit 8	Visit 9	Visit 10	Visit 11	Visit 12	Visit 13/EO T	Early Termin- ation (ET)

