-	Study Week		Week 0	Week 1	Week 2	Week 3	Week 4	Week 5	Week 6 or ET at week 6	Week 7	Week 8	Week 9	Week 10	Week 11	Week 12	Any visit other than at week 6
Medical His	tory	X														
Physical Ex	am	Х														
MINI		Х														
Pregnancy Test (Females only)		X														
Post-Screer Pregnancy Checklist	ning		X			Х			X			Х				
ECG		Х							Х						Х	Х
Labs (CMP, Panel, CBC CRP, IL6, T	, Hs- NFα)	X							X						Х	X (only CMP, Lipid panel, and CBC)
Lab (HbA10	C) ⁴	Х														
Vital Signs		X	Х	Х	Х	Х	Х	Х	Х	Х	Х	Х	Х	Х	Х	Х
Height		X	Х													
Weight		X	Х	Х	Х	Х	Х	Х	Х	Х	Х	Х	Х	Х	Х	Х
Waist Circumferer	nce		Х						Х						Х	
TLFB ¹		Х	Х	Х	Х	Х	Х	Х	Х	Х	Х	Х	Х	Х	Х	Х

VAS	Х	Х	Х	Х	Х	Х	Х	Х	Х	Х	Х	Х	Х	Х	Х
Urine Drug Screen	Х	Х	Х	Х	Х	Х	Х	Х	Х	Х	Х	Х	Х	Х	Х
Fagerstrom Test	Х							Х						Х	
Adverse Events		Х	Х	Х	Х	Х	Х	Х	Х	Х	Х	Х	Х	Х	Х
PANSS		Х						Х						Х	
SANS		Х						Х						Х	
CDRS		Х						Х						Х	
CGI-S and CGI-I ²		Х						Х						Х	
CSSRS	Х	Х						Х						Х	Х
QOL		Х						Х						Х	
EPS Scales (BAS, SAS, AIMS)		Х						Х						Х	
Drug dispensing		Х	Х	Х		Х		Х		Х		Х			
Supportive Counseling		Х	Х	Х	Х	Х	Х	Х	Х	Х	Х	Х	Х	Х	

1- TLFB at screening will be completed for the past 30 days. All other visits the TLFB will collect information for the past week.

2- CGI-I will not be administered at baseline. Only CGI-S is administered at baseline.

- 3- EOT end of treatment
- 4- Lab (HbA1C) will only be performed at the screening visit

5- If ET falls on week 6, the visit should follow regular week 6 protocol. If ET falls on any other visit, follow ET protocol

Informed Consent Process: All subjects will sign IRB approved informed consent form (ICF) prior to starting any study related screening procedures. The written informed consent will be obtained by authorized study personnel. The authorized study staff will explain the study objectives, risks and benefits and overview of the study procedures to all subjects as part of the consent process.

Eligibility Review: An eligibility review will be conducted by the investigator at each site as per the inclusion exclusion criteria listed in section D of the protocol. All subject eligibility criteria will be reviewed by UMass designee prior to subject randomization.

Demographics and Medical/Psychiatric History: Subject's demographics, medical and psychiatric history will be collected as part of the screening process. All patient medical and psychiatric history will be reviewed by the investigator.

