Any clinically significant change noted from screening or if an ECG is considered abnormal and clinically significant, it will be reported as an AE and will be appropriately recorded in both the source documents and the eCRF.

Laboratory Procedures: Most of the lab procedures will be done at the site. All blood work will be done as fasting.

Routine lab panels done at site include: Hematology (CBC with diff), comprehensive metabolic panel (CMP) and lipid panel. These labs will be assessed at screening, week 6 and week 12. Routine lab panels will be collected for subjects who are early terminated. Additionally, an HbA1c test will be conducted at screening only. Approximately four tablespoons of blood will be taken at each blood draw.

Lab samples for Hs-CRP, IL6 and TNF -alpha will be collected by sites and stored at -80F. It will be batch shipped to UMass every 6 months. These will be analyzed at UMass Memorial labs. CRP, IL-6 and TNF- α are well established inflammatory markers that are associated with both psychopathology and metabolic side effects in patients with schizophrenia. We will analyze how brexpiprazole treatment might affect these inflammatory markers.

Hematology (CBC)	Comprehensive metabolic panel	Lipid Panel
Hematocrit	Alanine transferase	Total cholesterol
Hemoglobin	(ALT)	Chol, HDL
Platelets	Albumin	Triglyceride
	Total protein	Chol, LDL

Routine Lab Assessments at site:

Red blood cell	Alkaline	Chol, VLDL
count	phosphatase (ALK-	Cholesterol/DL ratio
Total and	P)	
differential	Aspartate	
(absolute) white	transferase (AST)	
blood cell count	Bicarbonate	
	Blood urea nitrogen	
	(BUN)	
	Creatinine	
	Glucose	
	Potassium	
	Sodium	
	Chloride	
	Estimated	
	glomerular	
	glomerular filtration	
	rate (eGFR)	

Future Testing: Blood samples will be collected at screening, week 6 and week 12 for use in future research related to schizophrenia. All samples will be labelled with a study ID. Only members of the research team will be able to derive an individual's identity from their study ID code. The key to the code is stored on secure server and can only be accessed through password-protected computer Sub-sites will store these at -80F and batch ship them to the UMass Psychotic Disorders Research Program at UMass Medical School for storage and future extraction/genotyping. The lead site will store all samples indefinitely.

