- 3) Post-Screening Pregnancy Checklist (Week 3 and 9 only)
- 4) TLFB
- 5) AE review
- 6) Supportive counseling

End of Study / Discontinuation of Study Medication – When a participant who is randomized to brexpiprazole completes Visit 12 (or sooner for those discontinuing study medication), he or she will no longer receive medications through the study. There will need to be a discussion with the participant and his/her treatment provider as to whether or not the participant will continue on the study medication after the subject's study participation is over. For participants finishing the study at Visit 12, this discussion should occur about three weeks prior to the final visit. If the participant will continue on the study medication study medications following standard clinical practice. The monitoring and management of symptoms, therapeutic response and medication side effects will be the responsibility of the treatment provider.

Subjects who do not wish to continue on the study medication after the end of study, the treatment provider can begin to manage a cross titration off the study medication and on to either the antipsychotic medication prior to the study or a new antipsychotic medication following standard clinical practice. The monitoring and management of symptoms, therapeutic response and medication side effects will be the responsibility of the treatment provider.

Withdrawal of Subjects

Subjects are free to discontinue their participation in the study at any time and without prejudice to further treatment. The investigator must withdraw any subject from the study who requests to be withdrawn or fits the criteria below:

- 1) If subject meet any exclusion criteria after enrollment.
- 2) If subjects have laboratory results that meet the exclusionary criteria range during the study, the subject will have his/her labs repeated before being withdrawn from the study.
- 3) Subjects will be withdrawn from the study is there is an increase in their PANSS total score greater than or equal to 20 compared to their baseline total score at any point during the study.
- 4) Female subjects may be terminated from the study if they become pregnant at any time while participating in the study.
- 5) If at any time the study sponsor or research personnel at UMass decide to terminate the study, subjects' consent will be withdrawn involuntarily.

Early Termination Visit

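### The low-side exclusion limits for sodium and potassium sit at 1.1 times the lower limit of normal, so they exclude normal results and leave no valid floor for entry or withdrawal

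*Combined protocol and SAP*

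**What the plan says.** The table of exclusionary laboratory values in Section D gives sodium and potassium the same two-sided rule. The potassium row reads "<1.1 times the lower limit or >1.1 times upper limit of the reference range"; the sodium row opens identically, "<1.1 times the lower limit or >1.1 times upper". The table belongs to the exclusion criteria, which are introduced with "Each subject must not have the following exclusion criteria prior to randomization in the study".

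Section F, Withdrawal of Subjects, uses the same range again. The lead-in is mandatory: "The investigator must withdraw any subject from the study who requests to be withdrawn or fits the criteria below". Item 2 of that list says: "If subjects have laboratory results that meet the exclusionary criteria range during the study, the subject will have his/her labs repeated before being withdrawn".

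Both electrolytes are part of the comprehensive metabolic panel, which is run at each site. On timing, Section E (Laboratory Procedures) says: "These labs will be assessed at screening, week 6 and week 12". For entry there is a central check, in Section E under Eligibility Review: "All subject eligibility criteria will be reviewed by UMass designee prior to subject randomization". No part of the protocol gives a numerical reference range or a different low-side limit for either electrolyte.

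**The concern.** A low-side exclusion limit should lie at or below the lower limit of normal (LLN). A factor of 1.1 puts it above. It looks as though the factor suited to the upper limit was carried over to the lower one.

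The rule can be handled in two ways. If it is applied as printed, patients with normal sodium cannot enter under usual reference ranges, and a normal week-6 sodium confirmed on repeat would require withdrawal. The trial randomizes 50 to obtain 40 completers, so it has little room for spurious withdrawals. If staff disregard the printed rule, which is more likely, the protocol gives them no number for the point at which low sodium or low potassium bars entry or requires withdrawal. Four sites using their own laboratories could then settle on different cuts. Those who enroll patients with normal sodium would also, on paper, be enrolling ineligible subjects. The deviation table in Section H classes that as a major deviation unless an exception was obtained.

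**Working it through.** **Inputs.** The factor 1.1 on both limits is from Section D. The plan gives no cut in mmol/L, so there is no figure of its own to reproduce. All reference ranges below are assumptions.

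**General result, needing no outside figure.** As printed, the eligible window runs from 1.1 × LLN to 1.1 × ULN, where ULN is the upper limit of normal. For any positive LLN, 1.1 × LLN > LLN, so results from LLN up to 1.1 × LLN are normal yet excluded. If ULN/LLN < 1.1, the cut lies above the ULN and every normal result is excluded.

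**Share of in-range people excluded.** Where the cut falls inside the range, treat the range as the central 95% of a normal distribution: mean = (LLN + ULN)/2, SD = (ULN − LLN)/3.92, share = [P(X < 1.1 × LLN) − 0.025]/0.95.

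**Sodium.** For 135–145: 1.1 × 135 = 148.5, 1.1 × 145 = 159.5, and 145/135 = 1.074 < 1.1.

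| Assumed range | ULN/LLN | Low-side cut | In-range people excluded |
|---|---|---|---|
| 135–145 | 1.074 | 148.5 | 100% |
| 133–146 | 1.098 | 146.3 | 100% |
| 137–145 | 1.058 | 150.7 | 100% |
| 136–148 | 1.088 | 149.6 | 100% |
| 133–148 | 1.113 | 146.3 | 96% |
| 132–148 | 1.121 | 145.2 | 92% |

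**Potassium.** For 3.5–5.0: cut = 1.1 × 3.5 = 3.85, and the window is 3.85–5.50. Width excluded = (3.85 − 3.5)/1.5 = 23%. Mean 4.25, SD = 1.5/3.92 = 0.383, P(K < 3.85) = 0.148, share = (0.148 − 0.025)/0.95 = 0.129.

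| Assumed range | Low-side cut | In-range people excluded |
|---|---|---|
| 3.5–5.0 | 3.85 | 12.9% |
| 3.6–5.2 | 3.96 | 12.2% |
| 3.4–5.1 | 3.74 | 10.0% |
| 3.5–5.3 | 3.85 | 9.5% |
| 3.5–5.5 | 3.85 | 8.0% |

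**What may have been meant.**

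| Candidate | Sodium (LLN 135) | Potassium (LLN 3.5) |
|---|---|---|
| 0.9 × LLN | 121.5 | 3.15 |
| LLN/1.1 | 122.7 | 3.18 |
| LLN | 135 | 3.5 |

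The choice matters: a sodium of 128 is eligible under the first two and excluded under the third.

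**The case against.** The best counter-argument is that this is an evident slip with limited consequences. Several parts of it stand.

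- **Potassium is over-strict rather than unworkable.** Read literally, its floor keeps out every low value at the price of a low-normal band. Only the sodium row cannot be operated under usual ranges.
- **The literal text errs toward caution.** No patient with low sodium or potassium could enter under it. The missing floor arises only if staff set the text aside. That is likely for sodium, but it is an inference.
- **The likely intent can be guessed.** A tolerance of about 10% beyond each limit is the natural reading, and the two candidates of that kind nearly coincide. But the text does not say so, and a plain LLN cut cannot be ruled out.
- **Withdrawal exposure is narrow.** Week 12 is the final visit, so the scheduled trigger effectively operates once, at week 6, and only after a repeat.
- **Other safeguards exist.** The investigator judges every out-of-range result for clinical significance (Section H), significant unstable medical conditions are excluded separately (Section D), and a medical monitor reviews adverse events and eligibility issues (Section J). These reduce the safety risk, but none supplies a number. Central eligibility review may produce one consistent reading at entry, yet the reviewer also has no valid limit to apply, and Section F describes no central step for withdrawal. Case-by-case waivers cannot repair a criterion that catches nearly everyone.

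The percentages also depend on assumed ranges and, where the cut falls within the range, on a normal distribution. The algebra does not.

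**Conclusion.** The concern holds. Both rows exclude normal results under any reference range, and neither states a limit that marks an abnormally low value. On the assumed sodium ranges, 92% to 100% of in-range people are excluded, and all of them whenever ULN/LLN is below 1.1. On the assumed potassium ranges the figure is 8% to 13%. Because the same table governs mandatory withdrawal, this is a wrong decision threshold in an operative rule, and it must be corrected even though sites are unlikely to follow it literally. The harm is to eligibility, electrolyte safety limits, retention and deviation status. It does not reach the endpoints or the analysis model.

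**What to change.** Amend the low-side limit in the sodium and potassium rows of the Section D table so that each lies at or below the LLN.

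- **Potassium:** 0.9 × LLN is one option (3.15 on an assumed LLN of 3.5).
- **Sodium:** a factor closer to 1, or an absolute floor, would be preferable, because 0.9 × 135 = 121.5 is very permissive.

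These are clinical choices, and the sponsor's clinicians should set the values. Withdrawal item 2 in Section F refers back to the table, so it takes on the corrected limits without further change. The cost is two table cells in an amendment, with no added patients, visits or procedures.
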